Study protocol

Asthma and Type 2 Comorbidities

*Real-life Characterisation of Patients with Active
Asthma and Type 2 Asthma Comorbidities*

Date:

25 June 2018

Regeneron contact:

[name]

OPRI Pte Ltd
[name]

[name]
[name]
[name]
United Kingdom

[contact]
Web site <http://www.opri.sg>

Chief Investigator:

[name], Professor of Primary Care Respiratory Medicine and OPRI Director

[contact]

Office number: [name]

Skype ID: [name]

Email: [contact]

Project coordinator:

[name], Research & Operations Director

Observational & Pragmatic Research Institute

Office address: [name]

Direct number: [contact]

Email: [contact]

Study sponsor:

Regeneron

Sanofi

Primary contact

[name] [[contact]]

TITLE	Asthma and Type 2 Comorbidities
Subtitle	Real-life Characterisation of Patients with Active Asthma and Type 2 Asthma Comorbidities
Protocol version number	1.3
Medicinal product	Not applicable
Product code	Not applicable
Marketing authorisation holder	Not applicable
Marketing authorisation number	Not applicable
Study aims and objectives	
Phase 1 To identify common clusters of T2 type comorbidities in a real world active asthma population. To identify a limited set of comorbidity clusters for further investigation.
 
Phase 2 To describe the overlap between these clusters and between individual comorbidities within the clusters. This will include an investigation of the characteristics of each cluster by comorbidity severity and activity, eosinophil count and age. Patient demography, asthma severity, resource utilisation and costs will be compared within and between selected key clusters.

Country of study	United Kingdom
Author	OPRI Pte Ltd [name]

Table of Contents

List Of Abbreviations	5
1.0 Background	6
2.0 Study aims and objectives	7
2.1 Study aims.....	7
2.2 Study objectives	7
3.0 Study design	8
3.1 List of comorbidities of interest.....	8
3.2 Study design.....	8
4.0 Study population.....	9
4.1 Data sources	9
4.2 Inclusion and exclusion criteria	9
5.0 Study variables and study outcome definitions.....	11
5.1 Describing demographic and clinical variables	11
5.2 Identifying comorbidities of interest	13
5.3 Categorising comorbidity activity and severity	13

LAMA	Long-acting Muscarinic Antagonists
LTRA	Leukotriene Receptor Antagonists
OCS	Oral Corticosteroids
OPC	Optimum Patient Care
OPCRD	Optimum Patient Care Research Database
PEF	Peak Expiratory Flow
PSSRU	Personal Social Services Research Unit
QOF	Quality and Outcomes Framework
RDAC	Risk Domain Asthma Control
SABA	Short Acting Beta-Agonists
SD	Standard deviation

1.0 Background

An estimated 334 million people suffer from asthma worldwide.[1] National studies show wide variation in achieving optimal asthma control, varying between 0% to 30%.[2,3] In a recent OPCRD report on over 100,000 UK active asthma patients, 20% were controlled and 60% were partially controlled.[4]

An important molecular mechanism of asthma is type 2 inflammation.[5] Asthma patients frequently suffer from T2 type comorbid conditions such as atopic dermatitis, allergic rhinitis, chronic rhinosinusitis, and nasal polyposis.[6] Of these, allergic rhinitis may be the most common, with estimates of prevalence in asthma patients of 25% to 100%.[7,8] These conditions also frequently occur together in patients with asthma, and are more common in this group than in the wider population: the prevalence of co-morbid chronic rhinosinusitis and nasal polyps, for example, has been estimated at 7% in people with asthma and 4% in general population.[9]

T2 type comorbidities also recognised as important determinants of asthma management and prognosis as these are associated with inadequate disease control, higher health care use, and poor quality of life.[5] Studies from OPRI and others have reported that atopic dermatitis, for example, is associated with more frequent asthma attacks and more persistent asthma in comorbid patients.[10,11]

Because of the common underlying disease process, it has been suggested that successful treatment of one of these conditions might also improve related conditions. This was not demonstrated in a review of intranasal corticosteroids for allergic rhinitis and asthma control [12], but more recent treatments such as Dupilumab have shown promise in patients with moderate to severe atopic dermatitis and in those with persistent asthma. [13,14]

The frequency with which these related conditions co-occur/cluster in patients with asthma in the community has not yet been described, nor has the relationship of these comorbidity clusters with asthma severity, resource utilisation and cost.

2.0 Study aims and objectives

2.1 Study aims

To identify and characterise common clusters of T2-type comorbidities in patients with active asthma.

2.2 Study objectives

Phase 1: The primary objective is to estimate the frequency of each combination/cluster of T2 type comorbidities in a real world active asthma population, and to select, by consensus, a limited set of common comorbidity clusters for further investigation.

Phase 2: The primary objective is to describe the overlap between these clusters and between individual comorbidities within the clusters in terms of patient demography, and asthma severity, resource utilisation and costs.

3.0 Study design

3.1 List of comorbidities of interest

The nine T2-type comorbidities of interest are: atopic dermatitis; allergic rhinitis; chronic rhinosinusitis; nasal polyps; urticaria; allergic conjunctivitis; food allergy; eosinophilic oesophagitis; and anaphylaxis.

3.2 Study design

A two-phase historical cross-sectional and cohort study using routine electronic patient records from UK primary care practices. The study period will be 2010-2017 (or the latest available data). It will include patients with active asthma. In Phase 1 the frequency of each combination of comorbidities will be estimated using most recent clinical data available for each eligible patient. In Phase 2, the clinical characteristics and service use in a 1-year period after the date of co-morbidity assessment will be described for a pre-selected set of common comorbidity clusters.

[figure not shown]

Figure 1: Study design Phase 2

4.0 Study population

4.1 Data sources

Phase 1: The Optimum Patient Care Research Database (OPCRD)

- Contains anonymous, longitudinal medical records for 5.3 million patients from about 700 primary care practices across the UK.
- Includes patient-level diagnostic, clinical and prescribing information.

Phase 2: The OPCRD and the Clinical Practice Research Datalink (CPRD).

- The CPRD includes linked primary and secondary care (HES) data for approximately 300 UK primary care practices.
- The HES records from the CPRD are required to identify secondary care service use and costs, and for some measures of disease severity.

4.2 Inclusion and exclusion criteria

Inclusion criteria

Registered at a participating practice for at least one year prior to their index date and within the study period. In phase 1, the cross-sectional assessment of co-morbidity co-occurrence, the index date for each patient will be the earlier of the following dates: the last data collection from each practice and 6 months before patient deregistration (to avoid gaps in the clinical data due to late recording of patient deregistrations). For CPRD practices with linked HES data, the index date will be the earliest of the following dates: the last data collection from each practice, 6 months before patient deregistration, date of last HES record. In phase 2, the index date will be one year before the last data collection from each practice and 6 months before patient deregistration, to allow for one year of follow-up.

Patient had active asthma at their index date:

- a diagnosis of asthma at any time before their index date (using QOF Read codes: see Appendix 1); AND
- two or more prescriptions for an asthma medication in the preceding year.

Exclusion criteria

Any other chronic lower respiratory condition recorded at any time (Read coded: see Appendix 2). These are:

- Lung disease due to external agents, other than smoking, such as occupational agents.
- Active COPD (a Read code at any time + medication in the last year of follow-up).
- Bronchiolitis obliterans.
- Pulmonary fibrosis.
- Pulmonary hypertension.
- Cystic fibrosis

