5.3 Categorising comorbidity activity and severity

Many of the comorbidities can be further characterised as inactive or active, and mild or moderate/severe at the index date using prescribing and primary and secondary consultation data. A comorbidity will be defined as inactive in the year prior to the index date if it was not classified as active. Similarly, a comorbidity will be defined as mild in the year prior to the index date if it was not classified as moderate/severe.

Following a rapid review of the definitions applied by studies using routine patient data and prescribing guidelines, the following definitions were adopted.

Note on medications with more than one indication

The indication for a prescription may not be recorded as the time it is issued and some medications can be indicated for more than one of the comorbidities of interest. Following a review of the approaches used in other published studies, the diagnosis recorded closest in time to the initiation of the medication will be taken as the indication. Similarly, the reason for outpatient consultations is not routinely coded in HES data and individual hospital specialties may treat more than one of the comorbidities of interest (e.g. ENT treating both allergic rhinitis and chronic rhinosinusitis). Where this occurs we will attribute the outpatient consultation to the diagnosis recorded closest in time to the secondary care consultation.

Atopic dermatitis

Active: A primary or secondary care consultation in the previous year. Prescription of a topical corticosteroid in the previous year.

Moderate/severe: A primary or secondary care consultation in the previous year. Prescription of a medium- to high-potency topical corticosteroid in the previous year (see Appendix 6 for categorisation of topical corticosteroid preparations).

Allergic Rhinitis

Active: A primary or secondary care consultation in the previous year. Prescription of a nasal corticosteroid in the previous year.

Moderate/severe: A primary or secondary care consultation in the previous year. Three or more nasal corticosteroid in the previous year.

Chronic Rhinosinutis

Active: Always active as this is a chronic condition.

Moderate/severe: A primary or secondary care consultation in the previous year. Three or more nasal corticosteroid prescriptions in the previous year.

Nasal polyps

Active: Always active.

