Moderate/severe: A primary or secondary care consultation in the previous year. Three or more nasal corticosteroid in the previous year. Polypectomy at any time.

Urticaria

Active: A primary or secondary care consultation in the previous two years. Prescription of an oral antihistamine in the previous year.

Moderate/severe: A primary or secondary care consultation in the previous year. A double or greater dose of an oral antihistamine at any time prior to the index date.

Allergic Conjunctivitis

Active: A primary or secondary care consultation in the previous year. Prescription of any topical eye drop in the previous year.

Moderate/severe: A primary or secondary care consultation in the previous year. Two or more prescriptions of any topical eye drop in the previous year.

Food Allergy

Active: Always active.

Moderate/severe: A primary care consultation in the previous year. A secondary care consultation in the past two years. A prescription for adrenaline in the past 30 months (adrenaline has an 18-month shelf life). Anaphylaxis at any time.

Eosinophilic oesophagitis

Active: Always active (as long-term treatment required).

Moderate/severe: Always categorised as moderate/severe (differentiation not appropriate).

Anaphylaxis

Active: Always active (there is always a risk of a subsequent episode).

Moderate/severe: A secondary care consultation, ER attendance or hospital admission in the past year. A prescription for adrenaline in the past 30 months (adrenaline has an 18-month shelf life).

Sources

[1] How much of a topical agent should be prescribed for children of different sizes? Andrew A. Nelson, Alicia D. Miller, Alan B. Fleischer, Rajesh Balkrishnan, Steven R. FeldmaJ Dermatolog Treat. 2006; 17(4): 224–228.

[2] UpToDate (<https://www.uptodate.com/home>).

[3] Rapid reviews to identify comorbidity definitions used in other studies using routine patient data (see Appendices 13 and 14).

[5] Lucendo AJ, Arias Á, Molina-Infante J, Arias-González L. The role of endoscopy in eosinophilic esophagitis: from diagnosis to therapy. Expert Review of Gastroenterology & Hepatology. 2017; 11(12): 1135-1149.

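### Three look-back windows in section 5.3 exceed the one-year registration minimum, and missing history is scored as inactive or mild; the bias has one direction but is likely small

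*Protocol*

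**What the plan says.** Protocol section 4.2 sets the entry condition: "Registered at a participating practice for at least one year prior to their index date and within the study period".

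Section 5.3 sets the classification windows. Three rules with a dated window reach back more than 12 months:

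- Urticaria, activity: "A primary or secondary care consultation in the previous two years".
- Food allergy, severity: "A secondary care consultation in the past two years. A prescription for adrenaline in the past 30 months".
- Anaphylaxis, severity: the same 30-month adrenaline rule, which section 5.3 links to an 18-month shelf life.

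Three further severity criteria have no time limit: for urticaria, "A double or greater dose of an oral antihistamine at any time prior to the index date"; for nasal polyps, "Polypectomy at any time"; and for food allergy, any past anaphylaxis.

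The defaults are explicit. On activity: "A comorbidity will be defined as inactive in the year prior to the index date if it was not classified as active". On severity: "a comorbidity will be defined as mild in the year prior to the index date if it was not classified as moderate/severe". Neither allows for a window that is only partly observed.

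Section 6.9 recognises that record length varies and may affect observed prevalence. It assumes that the most relevant morbidity history stays in the record when a patient changes practice. To test this, it repeats the Phase 2 analyses in patients with at least five years of record history.

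**The concern.** A patient can enter with 12 months of registration and be judged on 24 or 30 months. If the earlier part is not in the record, no qualifying event can be found there, and section 5.3 turns that absence into a substantive class.

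Take a patient with anaphylaxis registered for 13 months, whose only adrenaline prescription was issued 20 months ago at another practice and did not transfer. The 30-month rule would count that prescription. Without it, and with no secondary care event in the past year, the patient is mild by default.

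The error runs only towards inactive or mild, and it depends on time at the practice. Section 6.4 tabulates inactive, active, mild and moderate/severe numbers for each comorbidity in Phase 2, and section 6.6 characterises the clusters by comorbidity severity and activity. Both would carry the error. Anaphylaxis is most exposed: apart from adrenaline, its severity criteria are all secondary care events in the past year, so fewer alternative routes can rescue a missed prescription.

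**Working it through.** The protocol gives no figure for registration length, turnover or record transfer, so there is none of its own to reproduce. The check has three steps.

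**1. Guaranteed cover at the minimum registration**

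| Rule (section 5.3) | Window | Guaranteed by section 4.2 | Unobserved if nothing transfers |
|---|---|---|---|
| Urticaria activity, consultation | 24 months | 12/24 = 50% | 12 months |
| Food allergy severity, secondary care | 24 months | 12/24 = 50% | 12 months, unless HES supplies it |
| Food allergy and anaphylaxis severity, adrenaline | 30 months | 12/30 = 40% | 18 months |

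Nasal polyps, food allergy and anaphylaxis are always active under section 5.3, so only urticaria can become inactive this way.

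**2. Share of patients with short registration (assumed turnover)**

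Assume a constant annual turnover h of 5%, 7% or 10%. Among patients with at least 12 months of registration:

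- Under 30 months: 1 − exp(−1.5h) = 7.2%, 10.0%, 13.9%.
- Under 24 months: 1 − exp(−h) = 4.9%, 6.8%, 9.5%.

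**3. Share of true positives missed**

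A true positive is a patient who would qualify on the criterion if the whole window were seen. Assume that no history transfers and no other criterion is met. Registration is 1 + u years, where u has density h·exp(−hu).

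*Adrenaline, regular renewal every 18 months (the shelf life in section 5.3).* A record of 1 + u years misses (0.5 − u)/1.5 of patients for u below 0.5, and none after that. At exactly 12 months this is 0.5/1.5 = 33%. Averaged over u:

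[0.5 − (1 − exp(−0.5h))/h] / 1.5 = 0.41%, 0.58%, 0.82% for h = 5%, 7%, 10%.

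*Adrenaline, irregular renewal at the same mean rate.* With Poisson prescriptions at r = 1/1.5 = 0.667 a year, the share missed is [exp(−r(1+u)) − exp(−2.5r)] / [1 − exp(−2.5r)] for u below 1.5. At exactly 12 months this is 40%. Averaged over u it is 1.2%, 1.7%, 2.4%.

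*Urticaria consultations.* The same formula applies with a window of 2 years in place of 2.5 and u below 1. Consultation rates are assumed.

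| Consultations per year | Missed at exactly 12 months | Average, h = 5% | Average, h = 10% |
|---|---|---|---|
| 0.25 | 44% | 1.0% | 2.0% |
| 0.5 | 38% | 0.9% | 1.7% |
| 1 | 27% | 0.6% | 1.1% |
| 2 | 12% | 0.2% | 0.4% |

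The ranges are therefore about 0.4% to 2.4% for adrenaline and 0.2% to 2.0% for urticaria consultations. An individual at the 12-month minimum can face a large chance of being missed, but few patients are close to that minimum.

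**The case against.** The strongest reply is that the protocol has already considered record length. Section 6.9 names it, states its assumption and tests it. Five years of history fully covers the 24- and 30-month windows, and choosing a sensitivity analysis over a restriction of the main analysis is a defensible preference. This stands in part: the issue was not overlooked. But section 6.9 is motivated by prevalence, not by dated activity and severity criteria, and it leaves the main tables and their defaults unchanged.

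Second, registration length is not record length. If history transfers as section 6.9 assumes, nothing is lost, and in linked patients HES can supply secondary care contacts whatever the practice. This stands, and it is why the figures above are upper values under their assumptions. The protocol does not say whether dated prescriptions and consultations are part of the history it expects to transfer.

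Third, section 5.3 does not state whether the listed criteria combine by *and* or *or*. Under *or*, a missing older record matters only when no other criterion is met, which reduces the effect further. This also stands.

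A reader might infer three stronger claims that the document does not support:

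- That 7% to 14% of patients are misclassified, or about 26,000 of the 260,000 HES-linked patients at 7% turnover (260,000 × 10.0%). That counts short registrations among all asthma patients. Misclassification needs the comorbidity, deciding evidence in the unobserved part, no transfer and no other qualifying criterion.
- That comorbidity classification is affected throughout. Only urticaria, food allergy and anaphylaxis have dated windows beyond one year; nasal polyps has only an unlimited one. The other five use one-year windows or fixed classes.
- That very young children are especially affected. A child whose record runs from birth has no earlier history to miss and is fully observed.

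**Conclusion.** The point holds in a limited form. For urticaria activity and for food allergy and anaphylaxis severity, the look-back in section 5.3 exceeds the minimum in section 4.2, and non-observation is scored as inactive or mild. The resulting error has one direction, and section 6.9 does not remove it from the main tables.

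The likely size is small: about 0.4% to 2.4% of true positives missed on the adrenaline criterion and 0.2% to 2.0% on the urticaria consultation criterion. This rests on assumed turnover of 5% to 10% a year, assumed prescribing and consultation patterns, no transferred history and no other qualifying criterion. Relaxing either of the last two lowers it, and full transfer makes it zero. It does not threaten the study's conclusions. It is worth correcting because the remedy is specific and cheap.

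**What to change.** In the Phase 2 activity and severity tables, add a flag for each affected comorbidity based on available record length rather than registration date:

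- 24 months for urticaria activity.
- 30 months for food allergy and anaphylaxis severity.

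Classify as now any patient who meets a criterion, or whose record covers the window. Report a patient who meets no criterion and whose record is shorter than the window as *not assessable*, not as inactive or mild. Treat children whose record runs from birth as fully observed. Keep the 12-month rule everywhere else.

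State in section 5.3 or 6.9 that the criteria without a time limit (polypectomy, double-dose antihistamine, past anaphylaxis) depend on record length and are examined through the five-year subset. Neither a 30-month nor a five-year record guarantees a lifetime history, so the flag should not be presented as solving that part.

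The cost is a few lines of protocol text, one derived variable and somewhat fewer patients in the affected tables. Under the assumed turnover and with no transfer, at most about 7% to 14% would be not assessable for the 30-month rules and 5% to 10% for urticaria activity. The actual number would be lower, because patients who meet a criterion stay in. No clinical definition changes.

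### The Phase 2 index rule, as worded, does not secure its stated year of follow-up or any HES coverage, the exclusions can use post-index records, and the outcome year is defined in contradictory ways

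*Protocol*

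**What the plan says.** Section 4.2 of the protocol contains three index rules.

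- **Phase 1.** The index is the earlier of the practice's last collection and six months before deregistration. The six months are there "to avoid gaps in the clinical data due to late recording of patient deregistrations".
- **HES-linked practices.** The rule takes the earliest of three candidates, listed as "the last data collection from each practice, 6 months before patient deregistration, date of last HES record". There is no one-year step back.
- **Phase 2.** "In phase 2, the index date will be one year before the last data collection from each practice and 6 months before patient deregistration". The purpose given for this rule is "to allow for one year of follow-up". There is no *earlier of* and no HES date.

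Registration is required only before index: "Registered at a participating practice for at least one year prior to their index date and within the study period".

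The exclusions in the same section cover "Any other chronic lower respiratory condition recorded at any time" and "Active COPD (a Read code at any time + medication in the last year of follow-up".

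The outcome year is described elsewhere, in ways that differ. Section 3.2 places Phase 2 service use in the year after the comorbidity assessment. Sections 5.4 and 6.7 place resource use and costs in the year before index. Section 5.4 also restricts secondary care to the latest year of HES data, without tying that year to the index date. Section 4.1 lists CPRD with HES as a source for Phase 2 only.

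**The concern.** The index date fixes eligibility, comorbidity status and the outcome window for every Phase 2 result. A rule that two programmers could code differently is therefore a defect in itself, and more so when one coding misses the purpose that the rule states.

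Three things are at stake.

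1. If use is measured forward from index, patients with less than a year of practice or HES data will appear to use less care than they do.
2. The only HES rule has no step back, and the rule for the phase that uses HES has no HES date. Neither secures a HES year after index. Section 6.1 expects about 260000 of 440000 CPRD patients to be linked.
3. Removing patients because of codes or medication recorded after index makes membership of the cohort depend on the future. The exclusion wording suits Phase 1, where index lies at or within six months of the end of the record. In Phase 2 the one follow-up year is the year after index.

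**Working it through.** **Inputs, all from Section 4.2.** Let L be the last practice collection, D deregistration and H the end of HES data, in months. The stated target is 12 months of follow-up. The six months before D are treated there as possibly incomplete, so *clean* follow-up is counted only to the earlier of L and D − 6.

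**Step 1: does the rule give 12 months?**

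Reading A takes each offset as written and uses the earlier date: index = min(L − 12, D − 6).
Reading B takes one year before the Phase 1 date: index = min(L, D − 6) − 12.

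| Patient | A: months to L or D | A: clean months | B: months to L or D | B: clean months |
|---|---|---|---|---|
| Still registered at L | 12 | 12 | 12 | 12 |
| Left 1 month before L | 11 | 5 | 18 | 12 |
| Left 3 months before L | 9 | 3 | 18 | 12 |
| Left 6 or more months before L | 6 | 0 | 18 | 12 |

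Example, D = L − 12. Under A, index = min(L − 12, L − 18) = L − 18, and D − index = 6. Under B, index = L − 18 − 12 = L − 30, and D − index = 18, of which 12 are clean.

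The stated 12 months is reproduced for everyone only under B. Under A it is reproduced only for patients still registered at L.

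**Step 2: HES coverage.** For a patient still registered, index = L − 12. If HES ends *lag* months before L, HES coverage after index is max(0, 12 − lag). The protocol does not give the lag. Assumed lags of 0, 3, 6, 9 and 12 months leave 12, 9, 6, 3 and 0 months. If the HES-linked rule were carried into Phase 2 unchanged, an index set by the HES date would leave 0 months of HES data after it. With index = min(L, D − 6, H) − 12, every linked patient has 12 months of HES coverage.

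**Step 3: which year is the outcome year?**

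| Section | Window for use and costs |
|---|---|
| 3.2 | year after comorbidity assessment |
| 5.4 and 6.7 | year before index |
| 5.4, secondary care | latest HES year, not tied to index |

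Under the backward window, the one-year registration rule covers the practice record. With index = L − 12, HES is complete for that year (L − 24 to L − 12) unless the lag exceeds 12 months; an assumed lag of 18 months leaves 6. Follow-up truncation does not arise.

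**Step 4: size, if the window is forward and Reading A applies.** Assume a share f of patients has 6 of 12 months and a constant rate of use. The shortfall in unadjusted mean use is 1 − [(1 − f) + 0.5f] = 0.5f. For f = 5%, 10%, 20% and 30% this gives 2.5%, 5%, 10% and 15%. These shares are assumptions. A flat half-year is also too severe for recent leavers, who have 9 to 11 months in the table above.

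**Step 5: exclusions.** One criterion has no upper time limit, and the COPD criterion looks to the end of follow-up. In Phase 2 both can reach past index, whichever outcome window is chosen.

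**The case against.** The strongest reply is that nothing is truncated. The sections that define resource use and specify the cost models look backward from index, and the registration rule covers that year. That stands: a reader might infer that annual use is necessarily understated, and the documents do not support it. They do not rule it out either, because Section 3.2 and the stated aim of the Phase 2 rule both look forward.

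The second reply is that the Phase 2 sentence simply puts a one-year step in front of the Phase 1 list, and its stated purpose makes Reading B the natural one. This is fair, and Reading B removes the practice follow-up problem. But the text does not say it, and Reading B still has no HES date.

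Third, a reader might infer that the HES date in "the last data collection from each practice, 6 months before patient deregistration, date of last HES record" is each patient's own last hospital contact, so that the year after index is empty of HES events by design. That requires a per-patient reading. A linked patient with no HES record would then have no such date, so a coverage date is at least as plausible. The wording is ambiguous, and the stronger claim is not established.

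Fourth, excluding on a lifetime code for another lung disease can be defended as removing misclassified asthma. That is a reason to report such an analysis. It does not justify leaving the time limit open without saying so, and it does not account for a COPD medication window that falls after index.

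Finally, the Phase 2 design figure is not shown and may display the windows. The text should still agree with itself.

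**Conclusion.** The point holds as a defect of specification. As worded, the Phase 2 index rule does not guarantee the year of follow-up it is meant to allow. It carries no HES bound, and the only HES rule lacks the step back and uses an ambiguous date. The exclusions permit removal on post-index information. The outcome window is contradictory across Sections 3.2, 5.4 and 6.7.

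Understated use is a conditional consequence: it needs the forward window together with either the literal index reading or a HES lag. The documents give neither the share of leavers nor the lag, so its size cannot be computed; the 2.5% to 15% range is illustrative. The number of patients affected by the exclusions is also not given. Nothing in the protocol shows that any error would differ between comorbidity clusters.

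The correction belongs before Phase 2 dates are coded. Section 7.0 indicates that the Phase 2 application for CPRD access is still to be submitted.

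**What to change.** 1. State one outcome window for service use and costs, and reconcile Sections 3.2, 4.2, 5.4 and 6.7 with it, including the HES year used for secondary care. This comes first, because moving the index date without it leaves the outcome year undefined.
2. If the window is forward, define the Phase 2 index as 12 months before the earliest of: last practice collection; 6 months before deregistration; and, for HES-linked patients only, the end of HES coverage. Replace the present HES date with that coverage date.
3. Whichever window is chosen, assess the exclusions only on records up to index, with COPD medication taken from the year before index. Report later COPD codes as a sensitivity analysis.

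The cost is rewording and recoding of dates, slightly earlier index dates, and a few patients lost because they lack a full registered year before the earlier index.
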